SPAROW STUDY PROTOCOL

Objectives:

1. To conduct a randomized control trial to examine the efficacy of an INTERACTIVE SMARTPHONE APP, customized for Singaporean women with recent GDM, in optimizing post-delivery weight and metabolic profiles compared with standard care.
 - Primary outcome: Restoration of booking weight if previous booking BMI = 23; Weight loss of 5% with respect to booking weight if BMI > 23
 - Secondary outcomes: Improved cardiometabolic and inflammatory markers: fasting and 2h post-glucose load plasma glucose in an oral glucose tolerance test, HbA1C, advanced glycation end-products, C-peptide, HOMA-IR, lipid profile, liver function, hsCRP, IL-6.2.
2. Evaluate the relative cost-effectiveness of this INTERACTIVE SMARTPHONE APP compared to standard care within the Singapore healthcare system in terms of improvements in quality of life, feasibility, acceptability, scalability and sustainability.

Design:

During the antenatal period, subjects will be informed about the study during regular NUH GDM consultations. After delivery, women will be offered the opportunity to join the study. Informed consent will be obtained at the 36-41 week follow-up visit or if the patient is admitted to hospital between 36-41 weeks of gestation. An appointment will be given for the first study visit at 6-12 weeks post-delivery. After delivery before discharge, subject's height and weight will be taken. Women will undergo a 75gm OGTT. Fasting blood would be stored for metabolic assessments. Validated questionnaires on health status, diet, physical activity, and quality of life as listed below in secondary outcomes will be obtained.

RANDOMIZATION:

Participants would be randomized after informed consent has been obtained to either STANDARD care or INTERACTIVE SMARTPHONE APP arms of the study. The team aims to randomize 200 subjects (n=100 in each arm) and estimate that a minimum of 64 subjects will complete the study in each arm. The team has factored in a total of 15% attrition from postnatal diagnosis of type 2 diabetes, voluntary attrition and lost to follow-up.

INTERVENTIONS:

A) STANDARD CARE ARM: Subjects in the standard care arm will be informed of their increased risk of developing type 2 diabetes in the future, and given general lifestyle advice to maintain a healthy weight, eat a well-balanced diet and do regular exercise during their 6-week postnatal visit. Women found to have impaired fasting glucose (6.1-6.9 mmol/L) or impaired glucose tolerance (2H post glucose of 7.8-11.0 mmol/L) will be issued a letter reinforcing lifestyle changes namely weight loss (if raised BMI), diet, exercise, and encouragement to consult a family physician to discuss the appropriateness of starting medications that can prevent the progression to type 2 diabetes, or restore the blood glucose to normal levels. Those with a normal OGTT result will just be informed that it is normal.

B) INTERACTIVE SMARTPHONE APP ARM: Participants will download the INTERACTIVE SMARTPHONE APP and will be briefed on its use by our team of nutritionists/ dieticians, exercise physiologists and lifestyle coaches. Patients will also be given a digital weighing

machine to chart their weight weekly if they do not already own one. About 4 months after delivery, participants will return to the outpatient clinic for OGTT, HbA1C, advanced glycation end-products, C-peptide, HOMA-IR, lipid profile, liver function, hsCRP, and IL-6 testing, as well as the same validated questionnaires that they had completed during their previous visit. This will be their last visit pertaining to the study and will be discharged from the study.

Methods:

For the main analysis, the primary outcomes are the proportion of women attaining a satisfactory weight at 4 months post-delivery. The team will aim for a minimally important effect of a doubling in the proportion of women who attain their target weight, corresponding to 40% of women in the intervention group attaining their target weight (or less) and 20% in the control group. For a standard power of 80% and alpha of 0.05, the sample size required in each group to detect this effect is 64 individuals. To account for a potential 15% attrition rate, the team aims to recruit 75 individuals in each group.

Subject's visits:

VISIT 1 (6-12 weeks postnatal): Blood taking: at 0hr and 2hr for oral glucose tolerance test. HbA1C, advanced glycation end-products, C-peptide, HOMA-IR, lipid profile, liver function, hsCRP, and IL-6. Questionnaires: Patients will be asked to fill up a series of questionnaires that will cover their health status, diet, physical activity, and quality of life. An optional 10ml of additional blood will be collected for storage for use in future studies regarding the management of recent gestational diabetes.

VISIT 2 (about 4 months postnatal): Blood taking: at 0hr and 2hr for oral glucose tolerance test. HbA1C, advanced glycation endproducts, C-peptide, HOMA-IR, lipid profile, liver function, hsCRP, and IL-6. Patients will be asked to fill up a series of questionnaires that will cover their health status, diet, physical activity, and quality of life. An optional 10ml of additional blood will be collected for storage for use in future studies regarding the management of recent gestational diabetes.

Details of investigations performed:

- Blood taking for: OGTT, blood metabolic markers (C-peptide, insulin, HbA1C, lipid profile, liver function, hsCRP), blood for future research
- Measurements: Height, weight
- Questionnaires:
 - 1) 3-Day food diary,
 - 2) Self-Efficacy to regulate eating habits questionnaire,
 - 3) Self-Efficacy to regulate exercise questionnaire,
 - 4) Health Education Impact (heiQ),
 - 5) RAND-12 health questionnaire,
 - 6) Health Expenditure questionnaire.

Inclusion criteria:

Female aged 21 years and above; Plans to deliver in NUH; Diagnosed with GDM antenatally (between 12-34 weeks gestation) defined using the 2013 World Health Organization criteria;

Has a smartphone and able to independently use a smartphone app; Willing to provide a blood sample; Able to give written informed consent; Able to speak and read English.

Exclusion criteria:

Subjects with type 1 and type 2 diabetes (including suspected cases diagnosed by an abnormal oral glucose tolerance test in the 1st and early 2nd trimesters of pregnancy); Drugs that affect glucose or lipid metabolism; Terminal or life threatening condition; Physical or mental condition that would prevent completion of a majority of study instruments.

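### The protocol gives two enrolment targets, 200 and 150 women, from the same 15% attrition and the same 64 completers per arm

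*Protocol*

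**What the plan says.** Two sections of the protocol state the size of the trial.

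- **RANDOMIZATION** says the study "aims to randomize 200 subjects (n=100 in each arm) and estimate that a minimum of 64 subjects will complete the study in each arm". It adds: "The team has factored in a total of 15% attrition from postnatal diagnosis of type 2 diabetes, voluntary attrition and lost to follow-up".
- **Methods**, in the sample-size paragraph, plans on "40% of women in the intervention group attaining their target weight (or less) and 20% in the control group". It continues: "For a standard power of 80% and alpha of 0.05, the sample size required in each group to detect this effect is 64 individuals". It then sets the target: "To account for a potential 15% attrition rate, the team aims to recruit 75 individuals in each group".

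The first target is 200 women and the second is 2 × 75 = 150. Both sections use 15% attrition and 64 per arm. Neither refers to the other, and nothing says that one figure replaces the other. Alpha is given as 0.05, without saying whether the test is one-sided or two-sided.

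**The concern.** The enrolment target fixes when recruitment stops and how much power the primary comparison has. Here the same two inputs, 64 completers and 15% attrition, sit beside two different targets. At 150 women, enrolment is complete under Methods but only 75% complete under RANDOMIZATION (150/200). If this stays unresolved, stopping at either point could be defended afterwards by citing the section that suits.

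The consequence for power depends on the sidedness of alpha. If the test is two-sided, the choice of target decides whether the stated 80% is reached. If it is one-sided, both targets reach 80%, and 50 women are enrolled beyond what the calculation asks for, with no reason given.

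**Working it through.** **Inputs, all from the protocol.** Response 0.40 (app) and 0.20 (standard care), alpha 0.05, power 80%, 64 evaluable per arm and 75 recruited per arm come from Methods. The 100 randomised per arm comes from RANDOMIZATION. The 15% attrition appears in both. Sidedness is not stated, so both cases are shown.

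**Step 1: reproduce the 64.** I used the pooled-variance formula for two proportions without continuity correction:

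n per arm = [z(α)·√(2·p̄·(1−p̄)) + z(β)·√(p₁(1−p₁) + p₂(1−p₂))]² / (p₁ − p₂)²

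Here p̄ = 0.30, so the two roots are √0.42 = 0.6481 and √0.40 = 0.6325. The squared difference is 0.04.

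- One-sided 0.05: (1.645 × 0.6481 + 0.842 × 0.6325)² / 0.04 = 63.86, rounded up to **64**. This is the protocol's figure.
- Two-sided 0.05: (1.960 × 0.6481 + 0.842 × 0.6325)² / 0.04 = 81.22, rounded up to **82**.

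Other common two-sided versions give 79 (unpooled), 81 (arcsine) and 91 (continuity-corrected). None gives 64.

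**Step 2: link the completers to the targets.**

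- 64/0.85 = 75.3. Strict rounding up gives 76, but the stated 75 is close enough: 75 × 0.85 = 63.75, about 64 completers.
- 100 × 0.85 = 85 completers, not 64. Falling from 100 to 64 would need 36% attrition (1 − 64/100).

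So 75 per arm follows from the stated inputs, and 100 per arm does not.

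**Step 3: power at each target.** Power = Φ{[0.20·√n − z(α)·0.6481] / 0.6325}, with n the completers per arm.

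| Target | Completers per arm | One-sided 0.05 | Two-sided 0.05 |
|---|---|---|---|
| 150 (75 per arm) | about 64 | 80.1% | 69.9% |
| 200 (100 per arm) | 85 | 89.1% | 81.8% |
| Difference | 21 | 9 points | 12 points |

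An exact binomial calculation for the same z-test agrees: 80.7% and 70.7% at 64 completers, 89.5% and 82.2% at 85.

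**Step 4: enrolment for 80% power, two-sided.** 82/0.85 = 96.5, rounded up to 97 per arm or 194 in all. That is 44 more than 150 and within 200.

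**The case against.** The strongest defence is that both sections share the same evaluable requirement. Methods asks for 64 per group at 80% power, and RANDOMIZATION gives 64 as a floor. With 85 expected completers the floor is met, so no sum is wrong in either place, and the 200 could simply be a margin of safety. The 64 also fits only a one-sided calculation, and on that basis both targets reach 80%. The fall to about 70% needs a two-sided test, which the protocol never states. Sidedness is also a separate matter: it would remain open if both sections said 150, and a statistical analysis plan that is not shown may settle it for the final test.

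Much of this stands. The loss of power is conditional and should be described that way, and the fault is better called a contradiction than a miscalculation. The contradiction itself remains. A floor of 64 is compatible with 100 per arm but does not explain it, and no margin is mentioned. The difference between recruiting and randomising does not help, because those recruited cannot be fewer than those randomised. Further losses are not available as an explanation either, since RANDOMIZATION calls its 15% a total and lists what it covers. A separate analysis plan could not make two targets in the protocol agree.

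**Conclusion.** The concern holds. The protocol states its enrolment target in two incompatible ways, 50 women apart, which is a third of the smaller figure. Only the 150 follows from the stated inputs. Planned power differs by 9 points (one-sided) or 12 points (two-sided) according to which target applies.

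Whether the stated 80% is at risk depends on facts the protocol does not give. It is missed only if the trial stops at 150 and the test is two-sided. At 200 it is met under either sidedness. These figures assume the 40% and 20% response rates, exactly 15% attrition in each arm, and an analysis of completers by a pooled two-proportion test. The contradiction between the targets needs none of these assumptions. It must be fixed, because the target determines when enrolment ends.

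**What to change.** The sponsor should say which target is operating. Both sections should then carry the same enrolment target, attrition rate, expected completers and sidedness, with the required size and power to match.

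- **200 women, two-sided 0.05.** In Methods, change the required number to 82 per group (97 after 15% attrition) and the target to 100 per group, with about 85 completers and about 82% power. In RANDOMIZATION, replace the 64 with about 85 expected completers; if a floor is kept, it should be the required 82.
- **150 women.** In RANDOMIZATION, change the target to 75 per arm with about 64 completers. In Methods, state that the 80% is at one-sided 0.05 if that was the planned test; otherwise restate power as about 70% at two-sided 0.05. The second course needs only an edit, but it gives up the 80% and should be acknowledged as a design decision.
- **200 women, one-sided 0.05.** Keep the required 64, state the sidedness, change the Methods target to 100 per group (about 85 completers, about 89% power), and give the reason for enrolling more than 75 per group.

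Each of these is a change of wording. Extra enrolment arises only if the trial has been working to 150 and 80% power is wanted two-sided: at least 44 more women, from 150 to 194.

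### Does writing the lifestyle advice and the handling of OGTT results only under the standard-care arm spoil the comparison with the app?

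*Protocol*

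**What the plan says.** The Objectives set out to test the app "in optimizing post-delivery weight and metabolic profiles compared with standard care". INTERVENTIONS then describes the arms in two paragraphs.

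- **Paragraph A (standard care).** Women are told of their raised diabetes risk and "given general lifestyle advice to maintain a healthy weight, eat a well-balanced diet and do regular exercise during their 6-week postnatal visit". Those with impaired fasting glucose or impaired glucose tolerance "will be issued a letter reinforcing lifestyle changes namely weight loss (if raised BMI), diet, exercise, and encouragement to consult a family physician", where medication may be discussed. "Those with a normal OGTT result will just be informed that it is normal".
- **Paragraph B (app).** "Participants will download the INTERACTIVE SMARTPHONE APP and will be briefed on its use" by dietetic, exercise and coaching staff. Women without a digital scale are given one for weekly weighing. "About 4 months after delivery, participants will return to the outpatient clinic for OGTT" and other blood tests, repeat the questionnaires and leave the study.

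Under Subject's visits, both study visits are listed with no restriction by arm: "VISIT 1 (6-12 weeks postnatal): Blood taking: at 0hr and 2hr for oral glucose tolerance test", and the same tests again at about 4 months.

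**The concern.** Paragraph A holds four elements of care: risk information, lifestyle advice, the letter for an impaired result and the notice of a normal one. Paragraph B holds none of them and does not say that standard care continues alongside the app. App-arm women have an OGTT at Visit 1 as well, but nothing written under their arm says how the result reaches them.

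Taken literally, the arms differ by more than the app. Controls receive advice, and some a letter, directed at weight (the primary outcome) and glucose (secondary outcomes). The letter can also lead to a discussion of medication, while drugs affecting glucose metabolism are an exclusion criterion. The observed difference would then mix the effect of the app with the effect of leaving these elements out, and a small or null result would be hard to interpret. The cost-effectiveness objective is touched too, because app plus standard care and app instead of standard care are different strategies with different costs.

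**Working it through.** **1. Are A and B exclusive lists?** Three places in the protocol bear on this.

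- The 4-month return, final questionnaires and discharge appear only under B, whereas Visit 2 under Subject's visits is for all women. If the paragraphs were exclusive, controls would have no endpoint visit and the primary outcome could not be compared. The paragraphs are therefore not exclusive.
- In paragraph A only the first sentence names the standard-care arm. The sentences on OGTT results speak of women found to have a given result. They stand inside A, so this is suggestive and not conclusive.
- RANDOMIZATION counts a postnatal diagnosis of type 2 diabetes among the reasons for attrition, with no restriction by arm. That implies results are read and acted on in both arms, at least in the diabetic range.

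**2. What would each reading estimate?**

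| Reading | App arm | Control arm |
|---|---|---|
| Add-on | app, briefing, scale, plus the elements of A | the elements of A |
| Replacement | app, briefing, scale | the elements of A |

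Both are randomised comparisons of an app strategy with standard care, which is what the Objectives ask for. Neither isolates the app from the briefing and the scale, since the protocol gives those only to the app arm.

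**3. Size on the replacement reading.** Let f be the share of women who receive an element and d ≥ 0 the gain, in percentage points, in their chance of reaching target weight. Assume d is the same with and without the app. If D is the difference when both arms receive the element, then

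difference when only controls receive it = D − f × d.

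Inputs from Methods: 40% in the app arm and 20% in controls, so the planned difference is 40 − 20 = 20 points. For the general advice f = 1 if every control receives it. For the letter the protocol gives no f, and it gives no d for any element. Purely as an assumed range, with f = 1 and D = 20:

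- d = 2: 20 − 1 × 2 = 18 points
- d = 5: 20 − 1 × 5 = 15 points
- d = 10: 20 − 1 × 10 = 10 points

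The reduction applies only if the 40% was set with the elements of A in both arms. If it was set for the app package by itself, the planned 20 points already refer to the replacement comparison and nothing is lost. The protocol does not say which. The direction is the same throughout: a helpful element given only to controls makes the app look less effective.

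**4. Time for the letter to act.** Four months is 4 × 365.25 / 12 / 7 = 17.4 weeks. Visit 1 is at 6 to 12 weeks, which leaves 17.4 − 12 = 5.4 to 17.4 − 6 = 11.4 weeks before the endpoint. This assumes that the letter follows directly from the Visit 1 OGTT. Paragraph A does not name that visit, so the link is an inference. The window limits the letter's effect on weight but does not exclude one.

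**The case for a change.** The best case for a change is that the content of each arm belongs in the protocol and no analysis plan can supply it later. Nothing in the text extends paragraph A to app users, and different staff could deliver different comparisons from the same wording. A conservative direction is also no full comfort: if the advice or letter works, a null result would say little about the app. One clarifying sentence would cost almost nothing.

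Much of this stands. The silence is real, the protocol is the right place for arm content, and the difficulty with a null result would exist on the replacement reading.

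It falls short on two points. First, the defect appears only if the literal reading is preferred, and the protocol's own placement of the 4-month visit undercuts that reading. Second, the gain claimed for a change, an effect attributable to the app alone, would not follow, because the briefing and the scale would still differ between arms. Recording medication starts in both arms is a matter for the case report form; its absence from a protocol this brief is not an error. The economic comparison can be costed on the care actually delivered, under either reading.

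**Conclusion.** No change to the plan follows. The protocol leaves unsaid whether the elements of paragraph A also reach app-arm women, and a clinical team would sensibly settle that for both arms. It does not say that these women go without. Whichever way it is settled, the randomised comparison is valid and answers the objective as worded, and no stated figure (20% and 40%, 64 completers per arm) has to be altered.

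The size of any distortion cannot be derived from the document. It is f × d points with d unknown throughout and f unknown for the letter, and it is zero if the elements reach both arms. Where it is not zero it works against the app. This rests on the advice and letter being helpful or neutral for weight, and on their effect being similar with and without the app. The trial report should describe what each arm received, so that readers know whether the app was tested as an addition to standard care or in place of it.

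### The 64 per group stated for 80% power fits only an undeclared one-sided 5% test; a two-sided test of 40% vs 20% needs 82 completers, and 64 gives about 70%

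*Protocol*

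**What the plan says.** In the protocol's Methods section the minimally important effect is a doubling of the proportion reaching target weight, "corresponding to 40% of women in the intervention group attaining their target weight (or less) and 20% in the control group". The sample size follows: "For a standard power of 80% and alpha of 0.05, the sample size required in each group to detect this effect is 64 individuals". The next sentence turns this into a recruitment target: "To account for a potential 15% attrition rate, the team aims to recruit 75 individuals in each group".

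The RANDOMIZATION section gives a different target, 200 women with 100 per arm. It keeps the same completer figure, since the team there "estimate that a minimum of 64 subjects will complete the study in each arm", and the same allowance: "The team has factored in a total of 15% attrition".

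The protocol nowhere states whether the test is one- or two-sided, and it names no test for the primary outcome.

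**The concern.** All inputs to the sample size are given except sidedness. An unqualified alpha of 0.05 is conventionally read as two-sided, and on that reading 64 per group is too few for 40% against 20%.

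The figure also carries forward. The 75 per group in Methods is 64 inflated for attrition, and RANDOMIZATION repeats 64 as the minimum expected number of completers. A trial that recruited to the Methods target would have a materially higher chance of missing its own minimally important effect than the protocol states. A trial that recruited 100 per arm and lost many more women than planned would still appear, from the text, to have 80% power with 64 left in each arm.

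**Working it through.** **Inputs** (Methods): p1 = 0.40, p2 = 0.20, mean 0.30, difference 0.20; alpha 0.05; power 80% (z = 0.8416); equal groups (RANDOMIZATION).

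**Formula** (two proportions, pooled variance under the null, no continuity correction):

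n per group = [z_alpha × √(2 × 0.30 × 0.70) + 0.8416 × √(0.40 × 0.60 + 0.20 × 0.80)]² / 0.20²

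The square roots are √0.42 = 0.6481 and √0.40 = 0.6325.

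**Reproducing the protocol's 64.** One-sided 5%, z_alpha = 1.645: [1.0660 + 0.5323]² / 0.04 = 63.86, so 64. One-sided power at 64 is 80.1%. The arcsine formula, one-sided, gives 63.25, also 64.

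**Two-sided 5%**, z_alpha = 1.960:

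| Formula | n per group |
|---|---|
| Unpooled variance | 78.49 → 79 |
| Arcsine | 80.30 → 81 |
| Pooled under the null | 81.22 → 82 |
| Pooled under both hypotheses | 82.41 → 83 |
| Log odds ratio | 84.99 → 85 |
| Log relative risk | 89.85 → 90 |
| Pooled with continuity correction | 91 |

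None is below 79, so 64 is not a matter of rounding or choice of formula.

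**Two-sided power at the sizes the protocol implies.** Power = Φ{[0.20 × √n − 1.960 × 0.6481] / 0.6325}. For n = 64 this is Φ{(1.600 − 1.270) / 0.6325} = Φ(0.521) = 69.9%.

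| Completers per group | How it arises | Two-sided power |
|---|---|---|
| 63.75 | 75 × 0.85 | 69.7% |
| 64 | stated requirement | 69.9% |
| 75 | 75 recruited, none lost | 76.7% |
| 82 | two-sided requirement | 80.4% |
| 85 | 100 × 0.85 | 81.8% |

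Exact enumeration for the uncorrected chi-square test gives 70.7% at 64, 80.7% at 82 and 82.2% at 85, so the approximation is not the cause of the shortfall. At 64 completers, two-sided power reaches 80% only if the true app-arm rate is about 42.8% instead of 40%.

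**Recruitment.** 82 / 0.85 = 96.5, so 97 per group, 194 in total. Against 150 (2 × 75) this is 44 more women; against 200 it is none. From 100 per arm, 82 completers allow 18% attrition, while 64 completers would mean 36%.

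**The case against.** The strongest reply is that 64 is not a miscalculation. It is the exact answer for a one-sided 5% test, the stated aim is directional, and the statistical analysis plan, which was not available, may declare such a test. The word standard in the sample-size sentence sits next to power and need not describe alpha. It is therefore established that 64 matches only a one-sided test, but not that the team meant a two-sided one. This stands as a limit on what can be said of intent. It does not rescue the sentence. The protocol itself gives alpha, power, effect and result, and a reader will take the unqualified alpha as two-sided. A one-sided 5% test is as lenient as a two-sided 10% test and has to be declared where the number is justified.

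Second, at 100 per arm with 15% attrition the trial is adequately sized even two-sided. This is correct, and on that target the defect is one of wording. However, the protocol also states 75 per group and does not say which governs.

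Third, the 64 in RANDOMIZATION is a forecast, not a rule accepting 36% attrition. That is fair. The point is only that the forecast gives no warning that power would be about 70% at that number.

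Fourth, 82 assumes an uncorrected test. With continuity correction the requirement is 91 completers (91 / 0.85, so 108 randomized), and two-sided Fisher power at 85 completers is about 78%. These are true, but the protocol's own 64 matches the uncorrected formula (one-sided with continuity correction would be 74), so the like-for-like two-sided figure is 82. They are a reason to name the test.

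**Conclusion.** The concern holds. As written, 64 per group does not give 80% power for 40% against 20% at an alpha of 0.05 read in the usual way. It gives 69.9% (70.7% exact), and 82 completers are needed. The protocol's figure is right only for a one-sided 5% test that it does not declare.

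The practical size depends on the recruitment target. If 75 per group governs, the risk of missing the planned effect is about 30% instead of 20%; even with no losses, power would be 76.7%. If 100 per arm governs and attrition is the planned 15%, power is 81.8%, and what is wrong is the stated requirement and the minimum of 64 completers.

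This rests on a two-sided test, the uncorrected pooled formula and the protocol's own rates of 40% and 20%.

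**What to change.** Declare the sidedness, name the test, and make Methods and RANDOMIZATION agree on one target.

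- **Two-sided test, 200 in total.** Replace the two sample-size sentences in Methods with: *For 80% power at a two-sided alpha of 0.05 (chi-square test without continuity correction), 82 completers are required in each group. Allowing for 15% attrition, at least 97 per group are needed; the team will randomize 100 per group (200 in total).* In RANDOMIZATION, change the minimum number of completers from 64 to 82 per arm. Cost: wording only. If a continuity-corrected or Fisher test is planned instead, recompute, because 100 per arm would then fall short of 80% at 15% attrition.
- **150 in total is the operative target.** Change the 200 (100 per arm) in RANDOMIZATION to 150 (75 per arm). Then either state the two-sided power as about 70% or declare that 80% applies to a one-sided 5% test; neither needs more women. Restoring 80% two-sided power instead means 194 women, 44 more than 150.
- **One-sided test, 200 in total.** Keep 64 as the requirement, state and justify the one-sided 5% level, and remove the 75 per group. Cost: wording only.

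The protocol does not show which target governs, so the sponsor has to choose among these.

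### Is the primary endpoint unmeasurable because neither description of the 4-month visit names a weight?

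*Protocol*

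**What the plan says.** The Methods section of the Protocol fixes the endpoint and its timing: "the primary outcomes are the proportion of women attaining a satisfactory weight at 4 months post-delivery". The target itself is in Objectives: "Restoration of booking weight if previous booking BMI = 23; Weight loss of 5% with respect to booking weight if BMI > 23".

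The 4-month attendance is described twice. Under Interventions, part B: "About 4 months after delivery, participants will return to the outpatient clinic for OGTT, HbA1C, advanced glycation end-products, C-peptide, HOMA-IR, lipid profile, liver function", followed by two inflammatory markers and the questionnaires. Under Subject's visits: "VISIT 2 (about 4 months postnatal): Blood taking: at 0hr and 2hr for oral glucose tolerance test", followed by the same laboratory panel, questionnaires and an optional stored sample. Neither names a weight, and Visit 1 does not either.

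Weight appears in three other places:

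- Design, with a time attached: "After delivery before discharge, subject's height and weight will be taken".
- Details of investigations performed, with no time attached: "Measurements: Height, weight".
- Interventions, part B, where app-arm women receive a digital weighing "machine to chart their weight weekly if they do not already own one". The standard care paragraph has no counterpart.

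**The concern.** A visit schedule decides what is collected, and an analysis plan cannot recover a variable that was never recorded. Here the schedule goes down to an optional storage tube yet omits the one variable on which the trial is sized. The only weight with a stated time is taken before discharge, which cannot serve as a 4-month outcome.

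The only repeated weights described are those charted at home in the app arm. If they were used to fill gaps at 4 months, the endpoint would be measured differently by arm, and would be missing more often in controls. Because success is a hard cut-off, at booking weight or 5% below it, modest differences between scales could move women across the line.

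The printed target rule adds a second worry. Taken at face value it covers a booking BMI of exactly 23 and anything above, so leaner women could not be classified and would drop out of the comparison.

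**Working it through.** **1. Is a 4-month weight planned?** Three parts of the Protocol need to be read together.

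| Source | Content | Tied to a visit? | Arm-specific? |
|---|---|---|---|
| Methods | Endpoint: weight target at 4 months | 4 months | No |
| Subject's visits, Visit 2 | Clinic attendance at about 4 months | Yes | No |
| Details of investigations performed | Bloods; height and weight; six questionnaires | No item is | No |

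The details list comes directly after the two visits and spells out what they involve. The visits mention questionnaires only in general terms, and this list names them. If the lack of a visit label meant that weight is unscheduled, the food diary, heiQ and RAND-12 would be unscheduled too.

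The two lists also complete each other on the laboratory side. The visits name HOMA-IR, IL-6 and advanced glycation end-products, which the details list omits. The details list names insulin, which the visits omit although HOMA-IR is calculated from it. Absence from one list is therefore weak evidence that an item is not collected. With the endpoint set at 4 months and every woman due in clinic at about that time, the natural reading is that she is weighed there.

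**2. Is the home scale an endpoint source?** It is mentioned once, inside the description of the app intervention, for weekly charting, and only for women who own none. Neither Objectives nor Methods links it to the outcome. To see what would be at stake if it were used, assume a 60 kg booking weight and a 1 kg offset between scales (neither figure is in the Protocol). The offset is 1/60 = 1.7% of booking weight. The 5% target is 0.05 × 60 = 3 kg, so the offset is 1/3 of it. That would matter, but only under a use of home weights that the Protocol does not describe.

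**3. Do women below BMI 23 lack a target?** As printed, the first group would contain only women at exactly 23, which makes no sense as a rule beside a second group above 23. Methods applies its 40% and 20% success rates to the women of each group without setting aside any who have no target. A less-than-or-equal sign lost in conversion explains the text fully.

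**4. Would a missing stratum have a size?** First the plan's own figure. With p₁ = 0.40, p₂ = 0.20, mean 0.30, power 80% (z = 0.8416) and alpha 0.05 from Methods:

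n = [z_α √(2 × 0.30 × 0.70) + 0.8416 √(0.24 + 0.16)]² / 0.20²

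- One-sided, z_α = 1.645: (1.066 + 0.532)² / 0.04 = 63.9, so 64 per group, as stated.
- Two-sided, z_α = 1.960: (1.270 + 0.532)² / 0.04 = 81.2, so 82 per group.

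The sidedness is a separate matter. For the present point, two-sided power is Φ{[0.20 √n − 1.270] / 0.632}. The Protocol gives no share of women below BMI 23, so 20% and 40% are pure assumptions:

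| Completers per arm | None excluded | 20% excluded | 40% excluded |
|---|---|---|---|
| 64 (stated minimum) | 69.9% | 60.0% (n = 51.2) | 48.1% (n = 38.4) |
| 85 (100 × 0.85) | 81.8% | 72.6% (n = 68) | 59.9% (n = 51) |

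These losses arise only if the equals sign is meant literally. The 69.9% in the first column comes from the sidedness, not from the target rule. If the sign is a conversion loss, nobody is excluded and the loss is zero.

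**The case for a change.** The strongest case for acting is that the undated height-and-weight line proves less than it seems to. It pairs the same two measurements as the pre-discharge weighing in Design, so that single occasion could satisfy it. It fixes neither the time, nor the scale, nor equal treatment of the arms. App logs exist in one arm only, and nothing in the text forbids using them when a clinic weight is missing. Naming the weight at Visit 2 would cost almost nothing.

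Part of this stands: the Protocol does not expressly attach weight to Visit 2 and does not say which recorded weight feeds the endpoint. But reading the line as discharge only would mean that the protocol defines a 4-month weight outcome, brings every woman to clinic at about 4 months, and then does not weigh her. That is a far less likely reading than a terse list. Unequal measurement is a possibility inferred from silence and not something the text prescribes. Which recorded weight enters the analysis is commonly settled in the statistical analysis plan, which is not available here, and scale and procedure belong in a study manual. A low cost of rewording does not by itself make the present wording an error.

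**Conclusion.** No change follows. The surviving point is a gap in detail: weight is a listed measurement for all participants, but its link to Visit 2 and its source are left implicit. A competent team fills that gap by weighing both arms at the clinic visit. The Protocol supports neither the view that the endpoint cannot be scored nor the view that a 4-month weight exists in one arm only. The target rule shows, most plausibly, a lost comparison sign, which a look at the PDF would settle.

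No effect on power or bias can be attributed to this point. The power losses above depend on a literal equals sign and an assumed 20% to 40% of women below BMI 23. The scale offset depends on an assumed 1 kg, an assumed 60 kg, and a use of home weights that the Protocol does not describe. The conclusion rests on reading the details list as applying to both visits and on the equals sign being a conversion artefact. If the PDF showed a true equals sign, the target rule would need a second look.
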